10.2 Study Early Discontinuation

DePuy Synthes Mitek Sports Medicine reserves the right to temporarily suspend or prematurely discontinue this study either at a single site, multiple sites, or at all sites at any time for reasons including, but not limited to, safety or ethical issues, inaccurate or incomplete data recording, non-compliance, or unsatisfactory enrollment with respect to quality or quantity. The study may also be discontinued on the basis of the interim data analysis, as described in Section 6: **Study Design**.

If the study is prematurely terminated or suspended, DePuy Synthes Mitek Sports Medicine or its representatives will inform the Investigators/institutions, and the regulatory authority(ies) of the termination or suspension and the reason(s) for the termination or suspension, in accordance with applicable regulatory requirement(s). The ED/IRB should also be informed and provided with reason(s) for the termination or suspension by DePuy Synthes Mitek Sports Medicine or by the Investigator/institution, as specified by the applicable regulatory requirement(s). In addition, arrangements will be made for the return of all unused investigational products and other material in accordance with Sponsor procedure for the study.

10.3 Subject Early Discontinuation

Every subject should be encouraged to remain in the study until they have completed the protocol-required 26 week follow-up period. If the subject discontinues prematurely from the study, the reason for discontinuation must be documented in the source documents and site files, and submitted via CRF.

Subjects who have discontinued prematurely will be included in the analysis of results; however they will not be replaced.

11.0 STATISTICAL METHODOLOGY / DATA MANAGEMENT

The following sections provide a general description of the statistical plan for the analysis of study data. A separate Statistical Analysis Plan (SAP) document that provides greater detail on data derivations and the analyses to be performed will be developed prior to the planned interim analysis. The SAP will be developed no later than 90 days following enrollment of the first

patient in the study. The SAP will reflect the protocol and any amendments that have been implemented at the time the SAP is finalized. Any deviations from the final SAP will be noted in the final clinical summary report.

11.1 Study Design

This study is a prospective, multi-center, double-blinded, randomized controlled trial comparing the treatment group (MONOVISC) to a control (Saline) for the purpose of demonstrating superiority. It is planned that a total of N=560 subjects will be enrolled using a 2:1 randomization (374 MONOVISC and 186 Saline). An interim analysis of the primary endpoint will be conducted after 74 patients in the MONOVISC arm and 37 patients in the Saline arm have completed their 26 week per protocol follow up visit. The study will be terminated if the mean WOMAC A1 pain change from baseline difference (MONOVISC minus Saline) is less than 0.4 in both the Per Protocol Analysis Set for the 26 week interval and the As Treated Analysis Set for the 26 week interval. If this difference is greater than 0.4 in favor of MONOVISC in either the Per Protocol Analysis Set for the 26 week interval or the As Treated Analysis Set for the 26 week interval, the study will continue to completion. Enrollment will continue throughout the time preceding and during the interim analysis.

Further description of the study design can be found in Section 6.0 above.

11.2 Treatment Assignment

The treatment groups in this study are:

MONOVISC: Two intra-articular injections of MONOVISC High Molecular Weight Hyaluronan, separated by 1 month (active treatment).

Saline: Two injections of 4 ml saline, separated by 1 month (control treatment).

Subjects will be randomized in a 2:1 ratio to receive either treatment with MONOVISC or treatment with Saline. Block randomization (random blocks of size 3 or 6) will be used to create a Master Randomization List, and patient kits of MONOVISC and saline will be sequentially numbered according to this list. With this randomization scheme, each study subject will be associated with a unique kit number, and the order of randomized subjects at each investigational site will be distinct. Prior to initiation of the study, investigational sites will be provided with an initial, sequentially numbered quantity of kits to be used, and as these kits are utilized, additional quantities of sequentially numbered kits can be ordered as needed through an electronic re-order system. The kit will not contain any labeling to indicate whether the patient is receiving MONOVISC or Saline. After the first injection, the remaining syringe will be returned to the storage site for the second injection.

All clinical research and biostatistics personnel at DePuy Synthes Mitek Sports Medicine will remain blinded to treatment assignment until the end of the study. An employee within Strategic Medical Affairs will be designated to maintain the Master Randomization, to facilitate any medical safety reviews, if necessary, and to facilitate the planned interim futility analysis.

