8.5.1 Randomization & Injection

Prior to the start of the study, a computer generated random list of treatment assignments (Master Randomization List) will be created using a 2:1 schema to either MONOVISC or saline injection, and patient kits of MONOVISC and saline will be sequentially numbered according to this list. Investigational sites will be provided with an initial, sequentially numbered quantity of kits to be used, and as these kits are utilized, additional quantities of sequentially numbered kits can be ordered by the site. With this randomization scheme, each study subject will be associated with a unique kit number, and the order of randomized subjects at each investigational site will be distinct. The syringe contents will be physically blinded. However, due to the difference in syringe plunger pressure required to eject MONOVISC compared to saline, the Investigator performing the injections will likely know whether they are injecting MONOVISC or saline. As such, a designated Injecting Investigator will be responsible for the injection of either MONOVISC or saline. Non-injecting Blinded Investigators will perform all follow-up evaluations to ensure that blinding is maintained. However, Injecting Investigators may participate in screening and pre-injection baseline evaluations.

Final enrollment anticipated:

- 374 subjects receiving two 4-mL injections of MONOVISC, separated by 1 month (active treatment)

- 186 subjects receiving two 4-mL injections of saline, separated by 1 month (control)

All clinical research and biostatistics personnel at DePuy Synthes Mitek Sports Medicine will remain blinded to treatment assignment until the end of the study. An employee within Strategic Medical Affairs will be designated to maintain the Master Randomization, to facilitate any medical safety reviews, if necessary, and to facilitate the planned interim futility analysis. This individual will be authorized to unblind a site for any patient in the event of an Adverse Event that requires treatment.

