The Injecting Investigator will obtain the next sequentially numbered patient kit from the secure storage area. The kit will not contain any labeling to indicate whether the patient is receiving MONOVISC or Saline. If the Investigator discovers the presence of a condition at the time of injection that would render the subject ineligible for study participation, the subject should not be injected and will be considered a screen fail; the patient kit will be returned to the storage area to be used with the next study subject. The ineligible subject should then receive the standard of care as determined by the enrolling Investigator. The reason for subject ineligibility will be documented on the Screening and Enrollment Log.

Prior to injection, sterile drapes or other suitable means should be used to block the patient's view of the injection and the imaging monitor. Under fluoroscopic or ultrasound guidance, the patient will receive an intra-articular hip injection of either MONOVISC or saline. Injection technique should follow established procedures for IA hip injection, such as those used for injections of corticosteroid or imaging contrast agents. Details of a typical image-guided injection procedure are described in Appendix C.

During intra-articular hip injections, it is common to use extension tubing to connect the syringe to the needle. However, due to the high viscosity of MONOVISC, it can be very difficult to inject the solution through such tubing. Moreover, some of the injected liquid can remain in the tubing rather than being injected into the joint. For these reasons, extension tubing should not be used for the intra-articular injections in this study.

The Injecting Investigator will evaluate and report any Adverse Events that occur as part of the injection procedure.

Identical post-injection instructions will be given to all subjects, regardless of randomization. Patients will be advised to refrain from rigorous physical activity for 48 hours post-injection. All subjects will be permitted to take acetaminophen (e.g. Tylenol) only (through the 26 week follow-up visit) if necessary, for the control of injection site pain or for general joint pain, at a maximum rate of 4000 mg in a 24 hour period. Acetaminophen use will be monitored at each subsequent follow-up visit as self-reported by the subject (Sec. 8.3)

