12.0 STUDY MANAGEMENT AND ADMINISTRATION

12.1 Investigator Responsibilities

12.1.1 Blinded Investigator

The Investigator that may screen and enroll subjects, but will not inject patients. He/she will be blinded to randomization and will be responsible for subject follow-up data collection and assessment of endpoints.

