12.1.2 Injecting Investigator

Injecting Investigator: The Investigator that actively treats (injects) enrolled subjects in the sequential order of patient kits which have been provided will not be blinded to treatment assignment due to obvious tactile differences in MONOVISC vs saline injections. The injecting Investigator may be an orthopedic surgeon, sports medicine specialist, rheumatologist, physiatrist, or primary care physician approved to participate in the study by the Clinical Sponsor, DePuy Synthes Mitek Sports Medicine. To maintain blinding, the injecting Investigator may not participate in subject follow-up data collection. *However, he/she may participate in patient screening, enrollment and baseline evaluation. He/she may also assess, report and treat adverse events that may occur as part of the injection procedures. He/she may also treat adverse events that are reported by the blinded investigator during follow-up visits.*

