5.1 Randomization

Subjects will be randomized in a 2:1 ratio to receive either treatment with MONOVISC or treatment with Saline. Block randomization (random blocks of size 3 or 6) will be used to create a Master Randomization List and patient kits of MONOVISC and saline will be sequentially numbered according to this list. With this randomization scheme, each study subject will be associated with a unique kit number, and the order of randomized subjects at each investigational site will be distinct. Prior to initiation of the study, investigational sites will be provided with an initial, sequentially numbered quantity of kits to be used, and as these kits are utilized, additional quantities of sequentially numbered kits can be ordered as needed through an electronic re-order system. The kit will not contain any labeling to indicate whether the patient is receiving MONOVISC or Saline. After the first injection, the remaining syringe will be returned to the storage site for the second injection.

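### Printed block sizes of 3 or 6, plus an unblinded injector who may take part in enrolment, leave a preventable selection-bias risk

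*Protocol*

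**What the plan says.** - **Allocation.** Protocol 11.2 sets the ratio: "Subjects will be randomized in a 2:1 ratio to receive either treatment with MONOVISC or treatment with Saline". It also gives the block sizes: "Block randomization (random blocks of size 3 or 6) will be used to create a Master Randomization List". SAP 5.1 has the same disclosure: "Block randomization (random blocks of size 3 or 6) will be used to create a" master list. SAP Table 1 confirms a single list without site stratification.
- **Supply.** Under 11.2, "investigational sites will be provided with an initial, sequentially numbered quantity of kits to be used", with later re-orders. Under 8.5.1 the injector fetches the next kit in number order.
- **Who knows the treatment.** Protocol 8.5.1 accepts that "the Investigator performing the injections will likely know whether they are injecting MONOVISC or saline", because of plunger pressure. Section 12.1.2 goes further and describes the injector as not blinded.
- **Who can influence entry.** Section 12.1.2 says of the injector that "he/she may participate in patient screening, enrollment and baseline evaluation". Section 12.1.1 gives the Blinded Investigator the same scope: "The Investigator that may screen and enroll subjects, but will not inject patients". Section 12.1.3 refers to the Blinded Investigator as the enrolling one. Exclusion criterion 30 is open investigator judgement.
- **Late exclusion.** If a disqualifying condition is found at the time of injection, 8.5.1 makes the patient a screen failure and "the patient kit will be returned to the storage area to be used with the next study subject".
- **Who sees the block sizes.** Investigators sign the protocol signature page (12.7), and the protocol is reviewed with them at site initiation (13.1).

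**The concern.** Randomisation protects the comparison only if nobody who influences entry can anticipate the next assignment. Here one person may know the past assignments at the site, the block sizes and the kit order, and may also have a say in who goes next. Patients expected to do well could be brought forward when MONOVISC looks likely and held back when saline looks likely, deliberately or not.

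The endpoint is one patient-rated pain item and the planned effect is 0.6 points, so a small prognostic tilt matters. The analysis would not routinely correct it. The primary model in SAP 13.4.1 contains treatment, visit and subject only. Age, gender and baseline pain enter a sensitivity model, and only if a significance test finds them unbalanced. Unmeasured prognosis is never addressed. A patient refused at the table also leaves the comparison altogether, because the MITT set is built from subjects in whom treatment was attempted.

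**Working it through.** **The plan's own figure.** With a difference of 0.6, SD 2.2, two-sided 0.05, 80% power and 2:1 allocation, the saline arm needs 1.5 × (1.960 + 0.842)² × 2.2² / 0.6² = 158.3, so 159, with 318 on MONOVISC and 477 in total. Noncentral-t power at 477 is 0.800. The sample size is reproduced and is not in question. The standard error of the difference is 2.2 × √(1/318 + 1/159) = 0.214. The documents give no figure for predictability.

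**Inputs.** Block sizes 3 and 6 and the 2:1 ratio come from 11.2. Patients per site: 560/40 = 14 (protocol, up to 40 sites) or 560/25 ≈ 22 (SAP 4, up to 25 sites). Assumed, because the documents are silent: the two sizes are equally likely; the injector recalls every earlier assignment at the site; where a site's kits start in the list; how re-orders are batched.

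**A hand check of one step.** The mean block length is 4.5. Expected adjacent saline–saline pairs per block: none inside a block of 3; 5 × (2/6)(1/5) = 1/3 inside a block of 6; (1/3)² = 1/9 across a boundary. The average is 1/6 + 1/9 = 5/18, or 0.0617 per position. Dividing by P(saline) = 1/3 gives P(saline after saline) = 0.185. So after one saline the next kit is MONOVISC with probability 0.815, not 0.667. Simulation gives the same 0.815, and 0.41 after three MONOVISC in a row.

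**Predictability over a site's enrolment.** The injector's probability for the next kit was updated by Bayes' rule after each assignment, over simulated site sequences. Ranges are for 14 to 22 patients. The last column, k, is the mean sign of the guess (+1 if P(MONOVISC) is above 2/3, −1 if below) in the MONOVISC arm minus that in the saline arm.

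| Supply assumption | Known with certainty | Best guess correct | k |
|---|---|---|---|
| One unbroken run, starting at a block boundary | 8.6–9.3% | 74.1–74.9% | 0.79–0.82 |
| One unbroken run, start unknown | 1.3–2.6% | 71.1–72.4% | 0.67–0.74 |
| Start unknown, separate batches of 6 (assumed) | about 0% | about 68% | about 0.5 |

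Always guessing MONOVISC is right 66.7% of the time.

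**Bias.** Suppose the patient entered is better by η NRS in expected change when MONOVISC is favoured, and worse by η when saline is favoured. Then bias = k × η. The null probability of a significant result favouring MONOVISC is Φ(bias/0.214 − 1.96), which is 2.5% without steering.

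- η = 0.1: bias 0.5 × 0.1 = 0.05 to 0.82 × 0.1 = 0.08; null probability about 4% to 6%.
- η = 0.25: bias 0.5 × 0.25 = 0.125 to 0.82 × 0.25 = 0.205; null probability about 8% to 16%.

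These are upper bounds for the given η: every site, every guess. Bias is proportional to the share of sites that steer, so a quarter of sites gives 0.205/4 = 0.05 at the top of the range.

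**Larger blocks.** With 6/9/12 and 14 patients per site, even if the sizes are known, certainty is 0 to 2.4% and the best guess is right 67.7 to 70.8% of the time. With the start known, k falls from 0.79 to 0.58, so at η = 0.25 the bias falls from 0.20 to about 0.14. Block size helps, but who enrols matters more.

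**The case against.** The strongest answer is that the protocol already has several barriers. Block size varies, kits are unlabelled, the coordinator is blinded and the injector is barred from follow-up data collection. An outside vendor supplies the K/L grade, and walking pain is rated by the patient. Section 12.1.3 treats the Blinded Investigator as the enroller, while 12.1.2 lets the injector participate only. Screening may precede injection by up to 30 days, so the next kit is often not settled at screening. The reason for a table-side exclusion is logged.

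Much of this stands as a limit on size, and it rules out one tempting reading: that the injector decides who is enrolled. The text does not say that. Nor does a returned kit reveal its contents, because nothing was injected from it. But none of these barriers prevents an unblinded injector from using past assignments. Several of them protect outcome assessment rather than entry. The 30-day gap helps little, since 8.5 has eligibility reconfirmed by an unspecified team member and intends baseline assessment, randomisation and injection for the same day, when the next kit is settled. The lack of site stratification does not remove the problem either, because consecutive kits at a site are still a run of the blocked list.

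A reader might also take 9% certainty and 0.20 NRS as the expected size. They are the worst case: a known block start, an unbroken run, and steering of 0.25 NRS on every guess at every site.

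**Conclusion.** The weakness is real and its size is uncertain. Each element is in the current text: disclosed small blocks, an unblinded injector, sequential kits, a role in enrolment, and reuse of a kit refused at the table. Under the stated assumptions about 0 to 9% of assignments could be known with certainty, and correct guesses rise from 67% to between 68 and 75%. The bias would be about 0.05 to 0.20 NRS for an assumed steering of 0.1 to 0.25 NRS everywhere, and proportionately less if fewer sites steer. The supply details and the steering size are assumptions that the documents neither confirm nor exclude.

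A reader might infer that the comparison is biased. The documents do not support that: they show an opportunity, not its use. The point is worth acting on because the remedy uses a role that the protocol already has.

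**What to change.** 1. In 8.5.1, 12.1.1 and 12.1.2, require the enrolling Blinded Investigator to make and sign the final eligibility decision before the kit is pulled, and take the injector out of enrolment decisions. This breaks the link between guess and entry at any block size.
2. From that signature the patient counts as randomised. A patient not injected afterwards is recorded as randomised and untreated, with the reason, and reported by arm; the kit is not reused. The decision whether to inject is unchanged; only the accounting changes.
3. Step 2 alone does not protect the primary comparison, because MITT still omits subjects in whom treatment was not attempted. Add to the SAP a sensitivity analysis that includes them, and state how their missing 26-week scores are handled.
4. Move the block sizes from 11.2 and SAP 5.1 to a restricted randomisation file. Investigators who already have the protocol will still know the current sizes, so this is secondary.
5. Use larger mixed blocks only if a further part of the list is still to be generated. On the same assumptions, 6/9/12 keeps certainty to at most about 3%. Kits already labelled stay as they are.

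Cost: amended wording, an occasional wasted kit, and a Blinded Investigator signature before each first injection. Sample size, endpoints and treatment do not change.

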11.3 Levels of Significance

Unless otherwise stated, confidence intervals will be 2-sided 95% confidence intervals, and *p*-values will also be 2-sided; *p*-values below 0.05 will be deemed to be statistically significant. Unless otherwise stated, there will be no adjustment of significance levels because of testing multiple hypotheses.

A primary endpoint interim analysis will be conducted after 74 patients in the MONOVISC arm and 37 patients in the saline arm have completed their 26 week follow-up visit to determine whether or not to stop the trial early for futility. This analysis will be based solely on the primary efficacy endpoint, and the trial will stop early if the mean WOMAC A1 pain difference (MONOVISC minus Saline) change from baseline is less than 0.4 in both the Per Protocol Analysis Set for the 26 week interval and the As Treated Analysis Set for the 26 week interval. Since this interim analysis does not have an early stopping rule for success, the final primary endpoint analysis will be conducted with a 2-sided p -value threshold of 0.05 for determining study success (no penalty for having conducted the interim analysis with futility stopping rule). Subject enrollment will continue during the interim analysis period.

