6.0 Study Design

This study is a prospective, multi-center, double-blinded, randomized, controlled, superiority study comparing intra-articular injections of MONOVISC High Molecular Weight Hyaluronan with intra-articular injections of physiologic saline. The study will take place at up to 40

investigational sites, primarily in the United States. Additional sites may be added in Canada and/or Europe. Subjects will be randomized through a 2:1 schema to receive either two (2) injections of 4 ml of MONOVISC, separated by 1 month (active treatment), or two (2) monthly injections of 4 ml of saline, separated by 1 month (control treatment).

Subjects will return for follow-up visits at 2, 4, 8, 16, and 26 weeks after the first injection.

The primary endpoint will be pain during walking (WOMAC A1) change from baseline at the 26 week time point.

An interim analysis of the primary endpoint will be conducted after 74 MONOVISC and 37 saline subjects have received both injections of MONOVISC or saline and completed their per protocol 26 week follow up visit. A stopping rule for futility will be implemented, such that the study will be terminated if the improvement of MONOVISC over saline (change from baseline) is less than 0.4 on a 10 point Numerical Rating Scale (NRS) in both the Per Protocol Analysis Set for the 26 week interval and the As Treated Analysis Set for the 26 week interval. If the improvement of MONOVISC over saline (change from baseline) is more than 0.4 NRS in either of these analysis sets, the study will continue to completion.

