11.7 Hypotheses

The primary endpoint analysis will be to demonstrate that the mean WOMAC A1 pain change from baseline for MONOVISC is significantly better than the mean WOMAC A1 pain change from baseline for Saline at 26 weeks after the first injection. The null (H_0) and alternate (H_A) hypotheses for this test of superiority are as follows:

$$H_0: \mu_{\text{MONOVISC}} \geq \mu_{\text{Saline}}$$

$$H_A: \mu_{\text{MONOVISC}} < \mu_{\text{Saline}},$$

where μ_{MONOVISC} is the mean WOMAC A1 pain change from baseline for MONOVISC at 26 weeks, and μ_{Saline} is the mean WOMAC A1 pain change from baseline for Saline at 26 weeks.

Decision Criterion: The primary endpoint analysis will be based upon a longitudinal model of all primary endpoint data from 2 weeks through 26 weeks; the adjusted means at 26 weeks from

this longitudinal model at 26 weeks will be compared. The decision will be made to reject the null hypotheses H_0 and conclude the alternative hypothesis H_A if the WOMAC A1 pain change from baseline adjusted mean for MONOVISC is less than the WOMAC A1 Pain change from baseline adjusted mean for Saline at 26 weeks, and the two sided p-value for the comparison of these adjusted means at 26 weeks is less than 0.05, or equivalently, if the entire 2-sided 95% confidence interval for the WOMAC A1 pain change from baseline adjusted mean difference (MONOVISC minus Saline), based upon the longitudinal model estimates, is less than 0. This primary efficacy endpoint analysis will be conducted on the MITT analysis set.

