11.9 Sample Size Justification

The sample size was determined based on the primary endpoint, which is a superiority comparison of WOMAC A1 pain change from baseline at 26 weeks for MONOVISC Subjects compared to Saline Subjects. Although it is planned to conduct the primary endpoint analysis with a longitudinal model, and to compare the WOMAC A1 pain change from baseline adjusted means at 26 weeks from this longitudinal model, the sample size was established based upon estimates for a t-test comparison of 26 week means for simplicity. Specifically, it is anticipated that the mean difference in WOMAC A1 pain change from baseline means will be at least 0.6 (where the mean for MONOVISC subjects is less than the mean for Saline Subjects), and that the standard deviation in WOMAC A1 pain change from baseline at 26 weeks will be approximately 2.2 in both groups. This standard deviation of 2.2 is consistent with published studies by Spitzer (2010) and Qvistgaard (2006); also, 2.2 is approximately $\frac{1}{4}$ of the maximum anticipated range of WOMAC A1 pain change from baseline, which would be an estimate of the standard deviation from data which are normally distributed. Using a two-tailed t-test and assuming a 2:1 randomization, the required sample size to yield 80% statistical power was estimated to be 318 MONOVISC and 159 Saline. With an anticipated attrition rate of 15%, the total study population was increased to be 560 patients (374 MONOVISC, 186 Saline). The sample size estimate was calculated with the following SAS code:

SAS Code for Power Estimation:
WOMAC A pain at 26 weeks

```
proc power;
  twosamplemeans
  meandiff= .6
  stddev=2.2
  groupweights=(2 1)
  power= .8
  alpha=0.05
  sides=2
  ntotal=.;
run;
```

The primary efficacy endpoint analysis will be conducted on the modified intent treat (MITT) Analysis Set with the handling of missing data at 26 weeks as described in Section 11.5 above. A supportive analysis will be conducted on the Per Protocol Analysis Set for Longitudinal Analysis.

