11.11 Plans for Interim Analysis

An interim analysis of the primary endpoint will be conducted after 74 subjects in the MONOVISC arm and 37 patients in the saline arm have entered the Per Protocol Analysis Set at 26 weeks. An early stopping rule for futility will be implemented in which the study will be terminated if the WOMAC A1 pain score change from baseline difference (MONOVISC minus Saline) is less than 0.4 in both the Per Protocol Analysis Set for the 26 week interval and the As Treated Analysis Set for the 26 week interval. If this difference is greater than 0.4 (which favors MONOVISC) in either the Per Protocol Analysis Set for the 26 week interval or the As Treated Analysis Set for the 26 week interval, the study will continue to completion.

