14.7 Possible Decisions or Actions Based on the IA Results

An early stopping rule for futility will be implemented in which the study will be terminated if the WOMAC A1 pain score change from baseline difference (MONOVISC minus Saline) is less than 0.4 in both the IA PP Analysis Set at 26 Weeks and the IA AT Analysis Set at 26 Weeks. All Patients already enrolled in the study at the time of the interim analysis will be followed to 26 weeks. No additional enrollment will be conducted. If this difference is greater than 0.4 (which favors MONOVISC) in either the IA PPP Analysis Set at 26 Weeks or the IA AT Analysis Set at 26 Weeks, the study will continue to completion.

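### The stop clauses of the interim futility rule use a contrast whose sign conflicts with the trial's own hypotheses, so the boundary does not have one reading

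*Protocol*

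**What the plan says.** **Direction of benefit.** WOMAC A1 runs from 0 (no pain) to 10 (worst), so a fall in score is improvement (Protocol 11.6). Protocol 11.7 declares success when the "adjusted mean for MONOVISC is less than the WOMAC A1 Pain change from baseline adjusted mean for Saline at 26 weeks" and the two-sided test is significant. Equivalently, the whole 95% interval for MONOVISC minus Saline must lie below 0. SAP 10 repeats this. Protocol 11.9 plans for a difference of 0.6 with the MONOVISC mean the lower one, which is -0.6 on that contrast.

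**Stop clauses.** Four places use the same named contrast with a positive threshold:
- Protocol 11.1: "The study will be terminated if the mean WOMAC A1 pain change from baseline difference (MONOVISC minus Saline) is less than 0.4"
- Protocol 11.3: "the trial will stop early if the mean WOMAC A1 pain difference (MONOVISC minus Saline) change from baseline is less than 0.4"
- Protocol 11.11: stop if the "WOMAC A1 pain score change from baseline difference (MONOVISC minus Saline) is less than 0.4"
- SAP 14.7: stop if the "change from baseline difference (MONOVISC minus Saline) is less than 0.4 in both the IA PP Analysis Set"

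Each requires the condition in both the Per Protocol and the As Treated 26-week sets.

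**Continue clauses.** Protocol 11.1 continues if the difference exceeds 0.4 in MONOVISC's favor in either set. Protocol 11.11 and SAP 14.7 continue if it exceeds 0.4 and add in parentheses that such a value favors MONOVISC. Protocol 11.3 has no continue clause and gives no direction.

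**Improvement wording.** Protocol 6.0 stops if "the improvement of MONOVISC over saline (change from baseline) is less than 0.4 on a 10 point Numerical Rating Scale", and SAP 4 says the same. SAP 14.2 names the interim variable as MONOVISC minus Saline and asks for it in improvement terms. SAP 14.6 analyzes the improvement of MONOVISC over Saline. The synopsis speaks of the separation between the arms.

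**The concern.** On the scale that decides the final analysis, a benefit is a negative number, and every negative number is less than +0.4. Taken by themselves, the four stop clauses are met by every result that favors MONOVISC. They are escaped only when MONOVISC is worse than saline by 0.4 or more.

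This is the trial's one planned interim stop/go rule. SAP 14.6 makes it mechanical: a point estimate is compared with a fixed boundary, without p-values or confidence intervals, by a team not otherwise involved in the study. Such a boundary should have one reading before anyone sees unblinded data. If the sign has to be settled afterwards, the decision is open to challenge whichever way it goes.

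**Working it through.** **Inputs.** Planned difference 0.6, SD 2.2 in both arms and 2:1 allocation (Protocol 11.9); two-sided 0.05 (Protocol 11.3); interim size 74 MONOVISC and 37 Saline (Protocol 11.11, SAP 14.3); boundary 0.4.

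**Plan's own figure.** Protocol 11.9 states that "the required sample size to yield 80% statistical power was estimated to be 318 MONOVISC and 159 Saline". Saline n = (1.960 + 0.842)² × 2.2² × (1 + 1/2) / 0.6² = 158.3, rounded up to 159. MONOVISC is then 318 and the total 477. The noncentral t gives power 0.8002 at that size, so the plan's figure is reproduced and its inputs can be used at the interim.

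**Interim standard error.** SE = 2.2 × √(1/74 + 1/37) = 0.443.

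**Two readings.** Let D be MONOVISC minus Saline in mean change from baseline, so that negative is benefit, and let d be its true value.
- Literal stop clause: stop if D < 0.4. P(stop) = Φ((0.4 − d)/0.443).
- Improvement reading: stop if Saline minus MONOVISC < 0.4, that is D > −0.4. P(stop) = 1 − Φ((−0.4 − d)/0.443).

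| True effect | d | Literal stop clause | Improvement reading |
|---|---|---|---|
| Planned benefit | −0.6 | Φ(2.26) = 98.8% | 1 − Φ(0.45) = 32.6% |
| No effect | 0 | Φ(0.90) = 81.7% | 1 − Φ(−0.90) = 81.7% |
| Equal harm | +0.6 | Φ(−0.45) = 32.6% | 1 − Φ(−2.26) = 98.8% |

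**How often the readings disagree.** Both stop when D lies between −0.4 and +0.4. Below −0.4 the literal clause stops and the improvement reading continues; above +0.4 the reverse holds. At the planned benefit the chance of opposite decisions is 67.4% + 1.2% = 68.6%. At no effect it is 18.3% + 18.3% = 36.6%.

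**Testing each clause with D = −0.6, the planned effect.**
- Protocol 11.1: −0.6 is less than 0.4, so the stop clause is met. It is also 0.6 in MONOVISC's favor, so the continue clause is met.
- Protocol 11.3: the stop clause is met, and nothing in that section says otherwise.
- Protocol 11.11 and SAP 14.7: the stop clause is met. The parenthesis that a value above 0.4 favors MONOVISC is false on the scale of Protocol 11.7.
- Protocol 6.0 and SAP 4: the improvement is 0.6, above 0.4, so the trial continues.

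**The case against.** The strongest reply is that the rule, read whole, has a clear intent. The continue clauses in Protocol 11.1, 11.11 and SAP 14.7 treat a value above 0.4 as favoring MONOVISC. Protocol 10.2 refers to Section 6 for discontinuation on the interim analysis, and Section 6 speaks of improvement. The separate interim team is set up by the SAP and would work from its Section 14. There, 14.2 asks for the difference in improvement terms, 14.6 analyzes improvement, and 14.7 applies the 0.4 boundary. An analyst following these in order would reach the intended decision.

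Most of this stands. A reader might infer from the stop clauses that the plan would stop a winning trial and let a harmful one run on. The documents do not support that: it requires isolating the stop clause and setting aside the continue clauses, Section 6 and SAP 14.2 and 14.6. Only Protocol 11.3 has no direction signal of its own. Nor is this the only way the trial can end, since Protocol 10.2 lets the sponsor discontinue for safety, data-quality, enrollment and other reasons.

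The reply does not show that the text is right. SAP 14.2 keeps the MONOVISC minus Saline label and gives no formula for turning it into an improvement, and the decision clause in 14.7 drops the improvement wording. The only formula for change written in the SAP, in the responder definition of 9.3, is visit score minus baseline score, on which improvement is negative. Further scoring detail is deferred to the shells, which SAP 15 requires only before final database lock, possibly after the interim.

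**Conclusion.** The point holds as an internal contradiction in a prespecified stop/go boundary. The stop clauses in Protocol 11.1, 11.3, 11.11 and SAP 14.7 conflict in sign with the hypotheses in Protocol 11.7 and SAP 10. The continue clauses in Protocol 11.1, 11.11 and SAP 14.7 signal the intended direction, but do so by contradicting the raw sign of the named contrast. The intended quantity is improvement, and the team would probably use it.

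What turns on the sign is large: stop probabilities of 98.8% against 32.6% at the planned benefit, and 32.6% against 98.8% at equal harm. The first figure in each pair is conditional on applying the stop clause alone and literally; it does not forecast what the team will do.

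The figures assume SD 2.2 at the interim, a normal approximation, and the Per Protocol and As Treated sets treated as one set of 74/37. Stopping requires both sets to fall below 0.4, so true stop probabilities would be somewhat lower where the sets differ. The 32.6% stop rate at the planned benefit under the intended reading comes from the threshold and the interim size, and is a separate matter from the sign.

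**What to change.** Before the interim data cut, define one signed quantity: Saline minus MONOVISC in mean WOMAC A1 change from baseline at 26 weeks, with positive values meaning benefit. State the rule on it in Protocol 11.1, 11.3 and 11.11 and in SAP 14.2 and 14.7: stop if it is below 0.4 in both the Per Protocol and the As Treated 26-week sets, otherwise continue. The word otherwise also covers a result of exactly 0.4, which the present less-than and greater-than clauses leave unassigned. Remove the MONOVISC minus Saline label from the interim text; it can stay in Protocol 11.7 and SAP 10, where it is used consistently.

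This keeps the sponsor's 0.4 threshold and the intent of Section 6. It costs a wording correction in the protocol and the SAP, and needs no additional patients or data.
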